1.1 Title

The Prevention of Chronic Obstructive Pulmonary Disease Exacerbations by Salmeterol/Fluticasone Propionate or Tiotropium Bromide (INSPIRE trial)

1.2 Intended aim(s)

The objective of the study is to compare the effect of the anti-inflammatory/bronchodilator combination of salmeterol/fluticasone propionate (SFC) with the bronchodilator tiotropium bromide on the rate of moderate and/or severe exacerbations during a 2-year treatment period, and secondarily on outcomes that might relate to exacerbations.

1.3 Primary endpoint for replication and RCT finding

Health care utilization exacerbation rate.

1.4 Required power for primary endpoint and noninferiority margin (if applicable)

With a sample size of 635 patients per treatment group, the trial will have 90% power to detect at least a 15% (equal to 1.445 exacerbations per subject per year) reduction in exacerbations in the SFC group at a two-sided significance level of alpha = 0.05

1.5 Trial estimate

Rate ratio = 0.967 (95% CI 0.836–1.119) comparing SFC to tiotropium bromide (Wedzicha et al., 2008, Am J Respir Crit Care Med). HR of 0.85 was used for power assessment based on RCT statistical analysis.

2. Person responsible for implementation of replication in Aetion

[name], ScM implemented the study design in the Aetion Evidence Platform. She is not responsible for the validity of design and analytic choices. All implementation steps are recorded, and implementation history is archived in the platform.

[figure not shown]
3. Data Source(s)

Optum Cliniformatics Data Mart, IBM MarketScan

4. Study Design Diagram

The study design diagram visualizes key aspects of the longitudinal study design for expediated review

Design Diagram - INSPIRE TRIAL REPLICATION

5. Cohort Identification

5.1 Cohort Summary

This study will involve a new user, parallel group, propensity score matched retrospective cohort study design comparing tiotropium to salmeterol. The patients will be required to have continuous enrollment during baseline period of 180 days before initiation of SFC or tiotropium inhalers (cohort entry date).

5.2 Important steps for cohort formation

New users (defined as no use in 180 days prior to index date) of an exposure and a comparator drug will be identified.

5.2.1 Eligible cohort entry date

SFC inhaler was first approved by FDA for market availability on August 24, 2000, and tiotropium on January 30, 2004

- Optum: January 30, 2004 March 31, 2020 (end of data availability is September 30, 2020 but excluded data generated during COVID-19 pandemic)
- Marketscan: January 30, 2004 December 31, 2018 (end of data availability)

5.2.2 Specify inclusion/exclusion criteria for cohort entry and define the index date

Inclusion and exclusion criteria were adapted from the trial as closely as possible. Definitions for all inclusion/exclusion are provided in **Appendix A** and are summarized in the flowcharts below.

5.3 Flowchart of the study cohort assembly

	OPTUM		MARKETSCAN	
	Less Excluded	Remaining	Less Excluded	Remaining
	Patients	Patients	Patients	Patients
All patients		79,335,559		200,203,908
Did not meet cohort entry criteria	-77,381,938	1,953,621	-196,683,354	3,520,554
Excluded due to insufficient enrollment	-308,951	1,644,670	-522,438	2,998,116
Excluded due to prior use of referent	-274,142	1,370,528	-362,567	2,635,549
Excluded due to prior use of exposure	-641,980	728,548	-1,225,388	1,410,161
Excluded because patient qualified in >1 exposure category	-10,386	718,162	-17,868	1,392,293

Excluded based on Missing/Unknown Age	-6	718,156	-1	1,392,292
Excluded based on Missing/Unknown Gender	-125	718,031	0	1,392,292
Excluded based on Inclusion #1 - Age 40 to 80 years old	-5	718,026	0	1,392,292
Excluded based on Inclusion #3a - Diagnosis of COPD	-471,394	246,632	-1,038,792	353,500
Excluded based on Inclusion #3b - Clinical history of at least 1 COPD Exacerbation	-110,352	136,280	-153,003	200,497
Excluded based on Exclusion #1 - COPD exacerbation in the 6 weeks prior	-33,666	102,614	-34,019	166,478
Excluded based on Exclusion #2a - Current asthma	-13,344	89,270	-13,539	152,939
Excluded based on Exclusion #2b - Current eczema, atopic dermatitis and/or allergic rhinitis	-5,978	83,292	-7,929	145,010
Excluded based on Exclusion #3 - Has a known respiratory disorder other than COPD	-15,367	67,925	-20,732	124,278
Excluded based on Exclusion #4 - Has narrow-angle glaucoma, prostatic hyperplasia or				
obstruction of the neck of the bladder	-3,927	63,998	-5,648	118,630
Excluded based on Exclusion #5 - Has undergone lung transplantation and/or lung volume				
reduction	-11	63,987	-41	118,589
Excluded based on Exclusion #7 - Requires regular (daily) long-term oxygen therapy (LTOT)	-2,422	61,565	-1,401	117,188
Excluded based on Exclusion #8 - Is receiving beta-blockers (except eye drops)	-7,770	53,795	-14,196	102,992
Excluded based on Exclusion #11 - Has evidence of alcohol, drug or solvent abuse	-945	52,850	-793	102,199
Excluded based on Exclusion #14 - Exclude use of Salmeterol, tiotropium, and fluticasone				
containing inhaler use	-591	52,259	-819	101,380
Final cohort		52,259		101,380

6 Variables

6.1 Exposure-related variables:

Study drug:

The study exposure of interest is initiation of SFC (LABA/ICS combination). Initiation will be defined by no use of inhaled SFC during the prior 180 days before treatment initiation (washout period).

Comparator agents:

Initiators of tiotropium inhaler defined as no use of inhaled tiotropium during the 180 days prior to index date

Patients are required to be incident users with respect to both exposure groups.

6.2 Preliminary Covariates:

- Age
- Sex
- Combined Comorbidity Index (CCI), measured over the default baseline covariate assessment period of 180 days prior to and including the index prescription date

Covariates listed above are a small subset of covariates that will ultimately be controlled in the design and analysis phase of the study. They are included in the preliminary assessment to determine the presence of adequate overlap between the two population of patients to proceed to the next phase of the study. Remaining covariates are defined only after the study has passed the initial feasibility analysis and initial power assessment and are listed in Table 1 (Appendix B).

6.3 Outcome variables and study follow-up:

6.3.1 Outcome variables

Effectiveness outcome variables of interest (definitions provided in **Appendix A**):

- Primary outcome: Healthcare utilization exacerbation rate per year (although the trial definition include 1) COPD hospitalizations or 2) exacerbations that required corticosteroids and/or antibiotics, in our emulation, we focused on 1) hospitalizations with COPD in the primary diagnosis position or 2) exacerbations that required corticosteroids. We did not include antibiotic use as part of the outcome definition because of our inability to determine whether the antibiotics were being used for COPD or some other indication)
- Secondary outcome:
 - All-cause death

Control outcomes of interest (control outcomes only serve to assess aspects of study validity but are not further interpreted): Pneumonia

6.3.2 Study follow-up

Both as-treated (AT) and intention-to-treat (ITT) analysis will be conducted with treatment defined as the index drug on the day of cohort entry. Because adherence in the real-world databases is expected to be much worse than in the trial, the AT analysis is the **primary** analysis, as it targets the relative rate of outcomes on treatment.

For the AT analysis, the follow-up will start the day after the initiation of SFC or tiotropium and will continue until the earliest date of the following events:

- The date of end of continued registration in the database,
- End of the study period or 730 days after cohort entry date,
- Death,
- Nursing home admission
 - Nursing home admissions are considered a censoring event because the data sources utilized typically
 provide little to no data on a patient, particularly on drug utilization, after admission. We will utilize this
 as an exclusion reason for cohorts for the same reason.
- The date of drug discontinuation, defined as the date of the last continuous treatment episode of the index drug (SFC or tiotropium) + a 60-day grace period,
- The date of switching from an exposure to comparator and vice versa,
- The date of switching to or initiation of other LAMA (excluding tiotropium) and switch or initiation to other LABA/ICS (excluding SFC), LAMA/LABA, LABA only, LAMA/LABA/ICS combination, and ICS only inhalers.

For the ITT analyses, the censoring based on the switching and treatment discontinuation will be replaced with a maximum allowed follow-up time of 365 days.

7 Initial Feasibility Analysis

Aetion report name:

Optum- https://bwh-dope.aetion.com/projects/details/1742/rwrs/71660
Marketscan- https://bwh-dope.aetion.com/projects/details/1741/rwrs/71658

Date conducted: 6/17/2021

Complete Aetion feasibility analysis using age, sex, and CCI as the only covariates and the primary endpoint (Section 6.3.1) as the outcome. No measures of association will be computed nor will incidence rates stratified by treatment group.

8 Initial Power Assessment

Aetion report name:

Optum- https://bwh-dope.aetion.com/projects/details/1742/rwrs/71659
Marketscan- https://bwh-dope.aetion.com/projects/details/1741/rwrs/71657

Date conducted: 6/17/2021

In order to complete the initial power analysis, the dummy outcome of a 90-day gap in database enrollment will be used. Complete a 1:1 PS-matched comparative analysis using this outcome. PS should include only 3 covariates: age, sex, and combined comorbidity index.

- Stop analyses until feasibility and power are reviewed by primary investigators and FDA. Reviewers evaluate the results of the analyses described above in Sections 7 and 8, including numbers of patients, patient characteristics, follow-up time, and reasons for censoring by treatment group, as well as overall rates of outcomes and study power. These parameters are re-evaluated and reported in the subsequent sections, after incorporating feedback and refining the protocol.
- Stop analyses until feasibility and power are reviewed by primary investigators, FDA, and assigned members of advisory board.

Reviewed by PI:	[name]	Date reviewed:	
Reviewed by FDA:	[name]	Date reviewed:	
Reasons for stopping			
analysis (if required):			

Effectiveness research with Real World Data to support FDA's regulatory decision making

9. Balance Assessment

Optum- https://bwh-dope.aetion.com/projects/details/1742/rwrs/72363
Marketscan- https://bwh-dope.aetion.com/projects/details/1741/rwrs/72364

Date conducted: 7/14/2021

After review of initial feasibility and power analyses, complete creation of the remaining covariates from Section 6.2. Again, using the dummy outcome of a 90-day gap in database enrollment, complete a 1:1 PS-matched analysis. The PS should include the complete list of covariates.

• Provide plot of PS distributions stratified by treatment group.

Note- Please refer to Appendix B.

• Report covariate balance after matching.

Note- For Table 1, please refer to Appendix B.

• Report reasons for censoring by treatment group.

	Overall	Referent	Exposure
Dummy outcome	0 (0%)	0 (0%)	0 (0%)
Death	706 (0.72%)	368 (0.75%)	338 (0.69%)
Start of an additional exposure	8,037 (8.18%)	4,562 (9.28%)	3,475 (7.07%)
End of Index Exposure	63,915 (65.03%)	29,311 (59.65%)	34,604 (70.42%)
Specified date reached	2,286 (2.33%)	1,069 (2.18%)	1,217 (2.48%)
End of patient enrollment	11,722 (11.93%)	5,877 (11.96%)	5,845 (11.89%)
Switch to other LABA, LAMA + LABA/LAMA combo + LAMA/LABA/ICS combo + ICS only + NH admissions Occurred	11,612 (11.82%)	7,952 (16.18%)	3,660 (7.45%)

• Report follow-up time by treatment group.

Patient Group	Optum Median Follow- Up Time (Days) [IQR]	Marketscan Median Follow- Up Time (Days) [IQR]
Overall Patient Population	88 [88, 162]	113 [88, 180]
Referent – Tiotropium	88 [88, 160]	99 [88, 175]
Exposure – Salmeterol/Fluticasone	88 [88, 165]	120 [88, 188]

• Report overall risk of the primary outcome.

·	Optum	MarketScan	Pooled
Risk per 1,000 patients	152.99	138.80	143.63

10. Final Power Assessment

Date conducted: 7/15/2021

• Re-calculate power in the appropriate excel table, using the revised number of matched patients from the PS-match in Section 9. All other parameters in the table should be the same as in Section 8.

	ı
Superiority Analysis (Pooled)	
Number of patients matched	
Reference	49,138
Exposed	49,139
Risk per 1,000 patients	143.63
Desired HR from RCT	0.85
Alpha (2-sided)	0.05
Number of events expected	14115.52551
Power	1

Superiority Analysis (Optum)	
Number of patients matched	
Reference	18,017
Exposed	18,017
Risk per 1,000 patients	152.99
Desired HR from RCT	0.85
Alpha (2-sided)	0.05
Number of events expected	5512.84166
Power	0.999976837

Superiority Analysis (Marketscan)		
Number of patients matched		
Reference	31,122	
Exposed	31,122	
Risk per 1,000 patients	138.80	
Desired HR from RCT	0.85	
Alpha (2-sided)	0.05	
Number of events expected	8639.4672	
Power	0.99999989	

• Stop analyses until balance and final power assessment are reviewed by primary investigators, FDA, and assigned members of advisory board.

Reviewed by PI:	[name]	Date reviewed:	
Reviewed by FDA:		Date reviewed:	
Reasons for stopping			
analysis (if required):			

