Appendix A: COPD Exacerbation (primary outcome), All-cause mortality (secondary outcome)

COPD Exacerbation

Measured 1 day after drug initiation in primary diagnosis position specified below and inpatient care setting -

COPD (Inpatient, Primary)

ICD-9 Diagnosis: 491.x, 492.x, 496 ICD-10 Diagnosis: J41.x, J42, J43.x, J44.x

OR

Measured 1 day after drug initiation in any diagnosis position specified below and inpatient and outpatient care setting AND steroid use within 14 days -

COPD (Any care setting, Any position)

ICD-9 Diagnosis: 491.x, 492.x, 496 ICD-10 Diagnosis: J41.x, J42, J43.x, J44.x

AND

Corticosteroid systemic administration and/or oral prescription of --

- Prednisone
- Prednisolone
- Methylprednisolone
- Dexamethasone
- Hydrocortisone

All-Cause Mortality

Identified using the discharge status codes-

Optum-Inpatient/Outpatient

- 20 = EXPIRED
- 21 = EXPIRED TO BE DEFINED AT STATE LEVEL
- 22 = EXPIRED TO BE DEFINED AT STATE LEVEL
- 23 = EXPIRED TO BE DEFINED AT STATE LEVEL
- 24 = EXPIRED TO BE DEFINED AT STATE LEVEL

- 25 = EXPIRED TO BE DEFINED AT STATE LEVEL
- 26 = EXPIRED TO BE DEFINED AT STATE LEVEL
- 27 = EXPIRED TO BE DEFINED AT STATE LEVEL
- 28 = EXPIRED TO BE DEFINED AT STATE LEVEL
- 29 = EXPIRED TO BE DEFINED AT STATE LEVEL
- 40 = EXPIRED AT HOME (HOSPICE)
- 41 = EXPIRED IN A MEDICAL FACILITY (HOSPICE)
- 42 = EXPIRED PLACE UNKNOWN (HOSPICE)

Marketscan-Inpatient

- 20 Died
- 22 Died
- 23 Died
- 24 Died
- 25 Died
- 26 Died
- 27 Died
- 28 Died
- 29 Died
- 40 Other died status or Expired at home (Hospice claims only) (depends on year)
- 41 Other died status or Expired in medical facility (Hospice claims only) (depends on year)
- 42 Other died status or Expired place unknown (Hospice claims only) (depends on year)
- 21 Died or Disch./Transf. to court/law enforcement (depends on year)

#	INSPIRE trial definitions	Implementation in routine care	References/Rationale	Color coding
			Please see the following Google drive for further details or any missing information_ https://drive.google.com/drive/fold ers/1WD618wrywYjEaXzfLTcuK-	
	Trial details - Intended S with label change - 2 weeks run-in		VCcnb6b-gV	Criteria
	EXPOSURE vs. COMPARISON			Adequate mapping in claims
	Tiotropium 18 mcg once daily vs. Salmeterol/fluticasone propionate (SFC) 50/500 mcg twice daily	SFC vs. Tiotropium		Intermediate mapping in

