		ICD-9 Diagnosis: 365.02, 36s.06, 365.2x
		ICD-10 Diagnosis: H40.03x, H40.2xx,
		Prostatic hyperplasia or obstruction of the neck of the bladder
I	Ulas paranu anala glaupama mastatia humanalasia ar abstruction of the mak of the hadder that in the continue of the	
4	Has narrow-angle glaucoma, prostatic hyperplasia or obstruction of the neck of the bladder that in the opinion of the	ICD-9 Diagnosis: 600.x
	investigator should prevent the subject from entering the study	ICD-10 Diagnosis: N40.x
		OR
		[
		At least one 30-day supply presciption claims for oral:
		Alfuzosin, doxazosin, tamsulosin, silodosin, finasteride 5 mg, dutasteride
ь		

[figure not shown]
_		Measured since all available data to and including the day of drug initiation in any diagnosis
		position in the inpatient and outpatient care setting
		Lung transplant
		ICD-9 Diagnosis: V42.6, 996.84
		ICD-10 Diagnosis: Z94.2, T86.810, T86.811, T86.819
		ICD-9 Procedure: 33.5x ICD-10 Procedure: OBYMOZO, OBYMOZ1, OBYMOZ2, OBYKOZO, OBYKOZ1, OBYKOZ2, OBYLOZO,
		OBYLOZ1, OBYLOZ2
5	Has undergone lung transplantation and/or lung volume reduction	CPT-4 Code: 32850 - 32856
		Lung volume reduction surgery (LVRS) ICD-9 Procedure: 32.22, 32.3x
		ICD-10 Procedure: 0BBC0ZZ, 0BBC4ZZ, 0BBD0ZZ, 0BBD4ZZ, 0BBF0ZZ, 0BBF4ZZ, 0BBG0ZZ,
		OBBG4ZZ, OBBH0ZZ, OBBH4ZZ, OBBJ0ZZ, OBBJ4ZZ, OBBK0ZZ, OBBK4ZZ, OBBL0ZZ, OBBL4ZZ,
		OBBMOZZ, OBBM4ZZ
		CPT/HCPCS codes: 32491, 32672, G0302, G0303, G0304, G0305
6	Female who is a nursing mother	
		Measured since all available data to and including the day of drug initiation in any diagnosis
		position in the inpatient and outpatient care setting
		LTOT
7	Requires regular (daily) long-term oxygen therapy (LTOT)	ICD-9 Diagnosis: V46.2
		ICD-10 Diagnosis: Z99.81
		CPT/HCPCS code: E0424, E0441, E0443
		Measured 180 days prior to and including the day of drug initiation with prescription for oral:
		Acebutolol, Atenolol, Betaxolol, Bisoprolol, Carteolol, Carvedilol, Labetalol, Metoprolol,
8	Is receiving beta-blockers (except eye drops)	Metiranolol, Nebivolol, Nadolol, Propranolol, Pindolol, Sotalol, Penbutolol, Oxprenolol
9	Has a serious, uncontrolled disease likely to interfere with the study	
10	Has received any other investigational drugs within the 4 weeks prior to Visit 1	
		Measured 180 days prior to and including the day of drug initiation in any diagnosis position in
		the inpatient and outpatient care setting
		Alcohol Abuse or Dependence

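### Was the nursing-home exclusion stated in Section 6.3.2 left out of the study cohort?

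*Combined protocol and SAP*

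**What the plan says.** Section 6.3.2 lists nursing-home admission among the events that end as-treated follow-up. The reason given is that the data sources record very little about a patient after admission, drug use above all. It adds that admission will be used "as an exclusion reason for cohorts for the same reason". For the ITT analysis, "the censoring based on the switching and treatment discontinuation will be replaced with a maximum allowed follow-up time of 365 days", so nursing-home censoring appears to remain there.

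Section 5.2.2 describes where criteria are documented: "Definitions for all inclusion/exclusion are provided in" Appendix A, with the flowcharts as the summary. The Appendix A table carries its own pointer to outside material: "Please see the following Google drive for further details or any missing" information. New use is "defined as no use in 180 days prior to index date" (Section 5.2).

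In Section 9, the last row of the censoring table pools switching to other inhaler classes with nursing-home admission. Its label ends "ICS only + NH admissions Occurred".

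**The concern.** The plan promises an exclusion and says where every criterion can be found, yet the flowchart has no line for it. The only entry about nursing in the legible part of Appendix A concerns nursing mothers. A reader could conclude that the matched cohort, Table 1 and the Section 10 power figures come from a population that should have been smaller.

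The plan's own reasoning gives the worry some substance. If drug claims vanish during a nursing-home stay, a stay in the 180 days before index could make a continuing user look like a new one, and could hide a steroid-treated exacerbation that Exclusion #1 should catch. A patient still resident after index might lack the steroid claims that define much of the primary outcome and the refills that drive as-treated censoring.

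The pooled censoring row adds to the unease. It mixes a reason that ITT drops with one that ITT keeps, and it differs sharply between arms.

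**Working it through.** **1. Flowchart (Section 5.3).** Inputs are the printed start, exclusion and remaining counts. All 20 subtractions reproduce in each database:

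- Optum: 79,335,559 − 79,283,300 = 52,259, as printed.
- MarketScan: 200,203,908 − 200,102,528 = 101,380, as printed.

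Nothing is left over for an unlisted step between rows. A step inside a row is a different matter. The first row, for failing cohort entry, removes 77,381,938 of 79,283,300 (97.6%) and 196,683,354 of 200,102,528 (98.3%). An exclusion coded as part of cohort entry would sit there and leave no trace. The numbered rows follow the trial's criteria, and nursing-home admission is not one of them.

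**2. Censoring table (Section 9).** 706 + 8,037 + 63,915 + 2,286 + 11,722 + 11,612 = 98,278, and each arm sums to 49,139. The pooled row is 7,952/49,139 = 16.18% for tiotropium and 3,660/49,139 = 7.45% for SFC, a ratio of 2.17. The row also covers switches to several other inhaler classes, so the whole contrast could come from switching. The nursing-home part may be anything from zero upward. Taking the full row as its upper limit would mean that nobody on that row switched inhalers, so it is not a useful bound.

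The table belongs to a run on a dummy outcome and reports as-treated censoring. Once ITT drops switching, nursing-home admission is the only component of that row left, so an ITT censoring table would show it separately.

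**3. Direction of the possible harm, rule by rule.**

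- Inclusion 3b (a past exacerbation): missing steroid claims can only make a patient fail, so they cannot admit an ineligible one. The criterion also looks back over all available data and has an inpatient route that needs no steroid claim.
- Residence at index: entry requires a dispensing of SFC or tiotropium seen in claims. On the plan's own premise, a current resident would seldom produce one.
- Washout and Exclusion #1: a missing claim could let a patient through. This route is real, but it needs a stay within the look-back, followed by a visible index claim, in a cohort where the stated exclusion was not run. The documents give no count for it. After matching, the mean frailty score is 0.17 in both arms and the mean comorbidity score 1.20 in both (pooled).

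**4. Power (Section 10).** Power = Φ(√(D/4) × |ln 0.85| − 1.96), where D is expected events.

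- Optum as planned: D = 36,034 × 0.15299 = 5,512.84; √(D/4) = 37.12; 37.12 × 0.1625 − 1.96 = 4.07; power 0.99998. The plan prints 0.999976837.
- Assumed event losses of 5%, 10% and 20%: D = 5,237, 4,962 and 4,410; power 0.99996, 0.99992 and 0.99971.
- MarketScan stays above 0.999999 throughout this range.
- For 90% power, D = 4 × ((1.2816 + 1.96)/0.1625)² ≈ 1,591. Optum would have to lose about 71% of its expected events to reach that.

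The losses are assumptions, chosen to show the range.

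**5. A related observation on oxygen.** Exclusion #7 removes 2,422 + 1,401 = 3,823 patients on long-term oxygen. The unmatched Table 1 still flags oxygen usage in 4,696 + 5,075 = 9,771 of 153,639 (6.4%). Appendix A defines the exclusion by two diagnosis codes and "CPT/HCPCS code: E0424, E0441, E0443". The codes and window behind the covariate are not in the text available. A covariate for oxygen use in general need not match a criterion for regular daily long-term therapy, so the two figures do not contradict each other.

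**The case for a change.** The strongest case is that Section 5.2.2 makes the flowchart the summary of all criteria, and that the flowchart is intact and prints rows as small as 11 and 41 patients (Exclusion #5). A small count would therefore not explain the missing row. The first review stop (Section 8) asks for reasons for censoring by arm, and the pooled row has the largest relative imbalance in the table, so on nursing-home admission it tells the reviewers nothing.

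Part of this stands. From the document alone, one cannot say where the exclusion was applied, over what look-back, or how many patients it removed, and nursing-home censoring by arm cannot be read from Section 9.

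What does not stand is the step from an absent row to an exclusion that was skipped. The design diagram is not shown in the copy reviewed, and Appendix A breaks off inside its last row, so silence there proves little. Section 2 says every implementation step is recorded and archived in the platform. Section 10 halts the work for review of balance and power. The question can be put and answered at that point.

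**Conclusion.** The observation is accurate, but it is a gap in traceability and not a fault in the design. The plan already contains the exclusion and the reason for it, and an analyst who follows Section 6.3.2 arrives at a sound cohort. The definition needed is the one already in use for censoring. If the archived history showed that the step had not been run, the error would be one of execution against a plan that already requires it.

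No printed count or power figure is shown to be wrong: the flowchart closes at 52,259 and 101,380, the censoring arms close at 49,139 each, and Optum power reproduces at 0.99998. The number of patients with a baseline nursing-home stay is unknown and cannot be bounded from the documents, and neither a direction of bias nor a difference between arms is established. The oxygen figures do not alter this. The conclusion assumes that the exclusion was run as Section 6.3.2 states, or will be before outcomes are analysed.
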